#### **Other Secondary endpoints**

6. Change in PROMIS® Emotional Distress – Depression Short Form (V1.0) T-score from baseline (randomization visit) to weeks 12 and 24 (key timepoint), and the 4 week post-treatment follow-up visit in the pomalidomide and placebo groups.
7. Change in PROMIS® Fatigue Short Form (V1.0) T-score from baseline (randomization visit) to weeks 12 and 24 (key timepoint), and the 4 week post-treatment follow-up visit in the pomalidomide and placebo groups.
8. Proportion of patients requiring no red blood cell transfusion or parenteral iron infusion during the 24 week treatment period in the pomalidomide and placebo groups.
9. Change in the ESS from baseline to that recorded at each individual patient assessment, including the 4 week post-treatment follow-up visit.
10. Change in the ESS from baseline to the average of the week 16, 20 and 24 assessments.
11. Proportion of patients requiring endoscopic interventions for management of bleeding during the 24 week treatment period in the pomalidomide and placebo groups.
12. Incidence and severity of adverse events in the pomalidomide and placebo groups including but not limited to:
  - Venous thromboembolism
  - Arterial thromboembolism
  - Thrombocytopenia
  - Neutropenia
  - Peripheral neuropathy
  - Fatigue
  - Constipation/diarrhea
  - Rash
  - Any other AEs or SAEs of at least moderate severity that are possibly related to pomalidomide
13. Change in iron/hemoglobin-related studies including iron saturation, ferritin, hemoglobin, hematocrit, MCV, and MCHC.

---

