# 8 ASSESSMENT OF SAFETY

## 8.1 SPECIFICATION OF SAFETY PARAMETERS

A secondary objective of this study will be to define the incidence of toxicities potentially attributable to pomalidomide. These include

- Venous thromboembolism
- Arterial thromboembolism
- Thrombocytopenia
- Neutropenia
- Peripheral neuropathy
- Fatigue
- Constipation/diarrhea
- Rash/pruritis

Venous and arterial thromboembolism will be considered serious adverse events and result in study drug discontinuation. Thrombocytopenia and neutropenia will be managed as outlined in Section 6.1.8. Peripheral neuropathy will be managed as outlined in Section 6.1.8.12. Management of fatigue will involve temporary withholding and/or dose reduction of study drug at the investigator's discretion.

The incidence of these toxicities has been determined in studies of patients with multiple myeloma, who have compromised bone marrow function, a predisposition to thrombosis, and reduced immunity. Therefore, estimates of toxicity based on this population are likely not relevant to the current study. However, subjects taking pomalidomide will be continuously monitored for these toxicities.

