Proportion of patients requiring endoscopic intervention through 24 weeks	Dichotomous (Yes/No)	
The number of endoscopic interventions for management of bleeding will be counted throughout the 24-week treatment administration. The outcome is calculated as “Yes” if ≥ 1 endoscopic intervention and “No” if no endoscopic interventions.
 
Endoscopic interventions are recorded by the site on the concomitant medications form, can be either nasal or gastroenterological interventions. Identification of endoscopic interventions (such as nasal cauter) will be confirmed by medical review. These were identified prior to database lock and include endoscopy, cauter, and embolization.

Incidence and Severity of Specific adverse events	Discrete	The incidence rate and maximum severity of the following adverse events will be calculated: MedDRA terms identified in blinded data review noted for each.

Variable	Type	Definition
		
 • Venous thromboembolism 
 ◦ Portal vein thrombosis, Deep vein thrombosis • Arterial thromboembolism 
 ◦ None found • Thrombocytopenia 
 ◦ Thrombocytopenia • Neutropenia 
 ◦ Neutropenia ◦ also Leukopenia, and also a category of (Neutropenia or Leukopenia) • Peripheral neuropathy 
 ◦ Neuropathy peripheral, Peripheral sensory neuropathy • Fatigue 
 ◦ Fatigue • Constipation/diarrhea 
 ◦ Constipation, Diarrhoea, Nausea, Abdominal pain • Rash 
 ◦ Rash popular, Rash pruritic, Rash maculopapular, Rash, Rash erythematous, Urticaria, Pruritus, Palmar erythema • Any other AEs or SAEs of at least moderate severity that are possibly related to pomalidomide and deemed medically relevant at masked data review: 
 ◦ Pulmonary embolism ◦ Mouth ulceration ◦ Alanine aminotransferase increased ◦ Tremor ◦ Dyspnoea and exertional dyspnoea (only the cases that meet criteria of at least possibly and at least moderate) ◦ Tachycardia (only the cases that meet criteria of at least possibly and at least moderate) ◦ Muscle spasms (only the cases that meet criteria of at least possibly and at least moderate)

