10 SAFETY ANALYSES

10.1 Overview of Safety Analysis Methods

All safety analyses will be performed using all participants in the safety population, regardless of eligibility. The frequency of toxicities potentially attributable to pomalidomide treatment will be determined (e.g., venous/arterial thromboembolism, thrombocytopenia, fatigue, constipation/diarrhea, rash). Treatment and resolution of all safety endpoints will also be documented. Treatment groups will be compared for incidence of events with a chi-squared or Fisher's exact test, and incidence density (events per person-months of exposure) will be calculated for toxicities in the pomalidomide group. Adverse event incidence rates will be included in semi-annual safety reports to the DSMB and annually to the FDA.

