10.2 Adverse Events

Per the protocol, participants were asked to report any adverse events from initiation of treatment through 24 weeks follow-up. All adverse events will be collected on an adverse event log and coded using MedDRA.

Adverse events will be listed and summarized by MedDRA system organ class and preferred term. Summaries will be of the number of events and number of individuals experiencing events by treatment group and will be created for all adverse events, by severity, and by relationship to treatment. Any events starting outside of the reportable time frame will be included in separate listings and will be excluded from summary tables. If a complete onset date is unknown and it cannot be confirmed that the event occurred during this time period, then the event will be considered a treatment-emergent adverse event.

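### SAP 9.2 counts nausea and abdominal pain under the protocol's constipation/diarrhea event, so the rate under that label describes a broader GI composite

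*SAP*

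**What the plan says.** Protocol 4.2.2, item 12, lists "Constipation/diarrhea" among the events whose incidence and severity are a secondary endpoint. Protocol 8.1 repeats it in the list meant to "define the incidence of toxicities potentially attributable to pomalidomide", Protocol 8.4.4 makes that list the adverse events of special interest, and Protocol 10.4.4 names it again for analysis. SAP 3.2.3, item 7, carries the label over unchanged.

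The outcome table in SAP 9.2 states that "The incidence rate and maximum severity of the following adverse events will be calculated", with "MedDRA terms identified in blinded data review noted for each". Under constipation/diarrhea the noted terms are "Constipation, Diarrhoea, Nausea, Abdominal pain". Under neutropenia, the same table has "also Leukopenia, and also a category of (Neutropenia or Leukopenia", that is, a separate added term and a labelled combination.

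SAP 10.1 says "Treatment groups will be compared for incidence of events with a chi-squared or Fisher's exact test". SAP 10.2 says "Adverse events will be listed and summarized by MedDRA system organ class and preferred term", with counts of events and of individuals by treatment group. SAP section 12 declares no departure from the protocol.

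**The concern.** Two of the four terms are not the event that the label names. If the terms are pooled, three results describe something wider than the protocol's endpoint: the incidence, the maximum severity and the arm comparison. A severe abdominal pain, for example, would appear as a severe constipation/diarrhea event. Nothing in the outcome table relabels the category or gives a reason for widening it, and no line restricted to constipation or diarrhoea is specified. A reader comparing the published row with the protocol would take it for the named toxicity.

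**Working it through.** The plan states no incidence or power for this event, so there is no figure to reproduce. The check is a comparison of texts, then a consequence that follows from the definition, then an illustration on assumed rates.

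**Texts side by side**

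- Event named in Protocol 4.2.2, 8.1 and 10.4.4 and in SAP 3.2.3: constipation/diarrhea.
- Terms in SAP 9.2: constipation and diarrhoea (the named event), plus nausea and abdominal pain (not the named event).
- Rash is a useful comparison. Pruritus under rash has a basis in Protocol 8.1 and 10.4.4, which pair the two. Nausea and abdominal pain have no such pairing with constipation/diarrhea.
- The SAP's category for other events requires at least moderate severity and a possible relation to drug. Under constipation/diarrhea, nausea and abdominal pain carry no such limit, so a mild, unrelated episode counts.

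**What follows from the definition**

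Let A be participants with constipation or diarrhoea, and B those with nausea or abdominal pain. The pooled category is A or B.

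- Incidence: P(A or B) = P(A) + P(B only), so it is never below P(A).
- Risk difference: pooled difference = difference in A + difference in B only. The second term can have either sign.
- Preferred-term rows: if c participants have constipation and d have diarrhoea, the number with either lies between max(c, d) and c + d. The rows do not fix it, because some participants may have both.

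**Illustration (all rates assumed)**

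Assume that A and B are independent, so pooled rate = 1 − (1 − a)(1 − b). Use the planned 53 placebo and 106 pomalidomide, and two-sided alpha 0.05, which is also assumed because the plan sets none for adverse events. Power is

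Φ{[|p1 − p0| − 1.96·√(p̄(1 − p̄)(1/n0 + 1/n1))] / √(p0(1 − p0)/n0 + p1(1 − p1)/n1)}

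where p̄ is the pooled proportion. As a check on the formula, it returns 98/96, 97/93 and 94/90%, as in Protocol Table 9. For 10% versus 30%: p̄ = 0.2333, null SE 0.0712, alternative SE 0.0607, and (0.200 − 1.96 × 0.0712)/0.0607 ≈ 1.00, which gives 84%.

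Each pair is placebo, then pomalidomide; RD is in percentage points.

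| Constipation or diarrhoea | Nausea or pain | Pooled | RD | Risk ratio | Power |
|---|---|---|---|---|---|
| 10%, 30% | none | 10.0%, 30.0% | 20.0 | 3.00 | 84% |
| 10%, 30% | 10%, 10% | 19.0%, 37.0% | 18.0 | 1.95 | 65% |
| 10%, 30% | 20%, 20% | 28.0%, 44.0% | 16.0 | 1.57 | 50% |
| 10%, 30% | 30%, 30% | 37.0%, 51.0% | 14.0 | 1.38 | 38% |
| 10%, 30% | 10%, 25% | 19.0%, 47.5% | 28.5 | 2.50 | 96% |
| 10%, 30% | 25%, 10% | 32.5%, 37.0% | 4.5 | 1.14 | 8% |
| 10%, 10% | 10%, 25% | 19.0%, 32.5% | 13.5 | 1.71 | 43% |

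Equal added rates shrink the contrast, and unequal ones can enlarge it or nearly remove it. In the last row a 13.5-point difference appears although the named event does not differ at all.

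The scale matters too. With rates of 12% versus 30% and a further 12% per arm who have only nausea or pain, the pooled rates are 24% and 42%. The risk ratio falls from 0.30/0.12 = 2.5 to 0.42/0.24 = 1.75, but the risk difference stays at 18 points (30 − 12 = 42 − 24).

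**The case against.** The case on the other side is substantial.

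- **Preferred-term tables.** SAP 10.2 reports each term by arm, also by severity and by relationship to treatment. This stands, and a reader who fears that a constipation or diarrhoea signal will be hidden is not supported by the plan. Only the either-event count is missing from the specified summaries.
- **Clinical coherence.** A reader might call the added terms unrelated. Protocol 2.3.1 lists GI intolerance as a known risk, and the endpoint list is expressly open-ended, so reporting nausea and abdominal pain is within scope. What does not fit is reporting them under a narrower name.
- **Selection.** The terms were fixed at blinded review and are disclosed, so there is no ground for suspecting choice by arm.
- **Inference.** SAP 7.7 places other secondary outcomes outside statistical significance, and the halting rule concerns thromboembolism only. No efficacy or stopping decision turns on this row.
- **Pooling is inferred.** SAP 9.2 does not say outright that the terms form one count, and the table shells are in a separate document (SAP section 14). Pooling is still the natural reading of a term list given for each named event.
- **The neutropenia contrast.** Showing leukopenia separately was one display choice and sets no rule. It does show that a workable layout already exists in the same table.

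**Conclusion.** The point holds as a minor one of definition and labelling. As written, SAP 9.2 yields a rate, a maximum severity and an arm comparison for a broader GI composite under the name of a narrower protocol event, while SAP section 12 records no change.

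The incidence under the label can only equal or exceed that of the named event. A reader might go further and infer that the pooling dilutes a true drug effect. The documents do not support that: they give no rates for any of the four terms, and the contrast can move either way, as the illustration shows. The size of the distortion is unknown. The tabulated figures rest on assumed rates, independence and planned sample sizes, and show only what is possible.

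The conclusion assumes that the four terms are pooled into one participant count. If the table shells already show a line for constipation or diarrhoea alone, only the wording of SAP 9.2 needs correcting.

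**What to change.** In SAP 9.2, define constipation/diarrhea by the preferred terms Constipation and Diarrhoea only, counting each participant once. If the four-term grouping is wanted, keep it as an additional category with its own GI label, following the layout used for neutropenia and leukopenia. Record that added grouping in SAP section 12 as a change from the protocol. Nausea and abdominal pain need no further work, because SAP 10.2 already tabulates them by arm.

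The cost is SAP wording and one or two table rows. No new data are needed, and neither the design nor the alpha allocation changes.

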12 CHANGES TO THE ANALYSES PLANNED IN THE PROTOCOL

The SAP expands the analysis of the primary and second endpoints described in the protocol. No changes from that specified in the protocol were made.

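### The SAP narrows the protocol's residual adverse event category with an undefined relevance filter and a closed list of seven items, and does not declare the change

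*SAP*

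**What the plan says.** Protocol 4.2.2, item 12, is a secondary endpoint. It is introduced as "Incidence and severity of adverse events in the pomalidomide and placebo groups including but not limited to" and followed by named toxicities, from venous thromboembolism to rash. The last bullet is a residual category: "Any other AEs or SAEs of at least moderate severity that are possibly related to pomalidomide". It has two conditions and no list of terms.

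SAP 3.2.3 repeats the bullet with a further clause. SAP 9.2 carries the same clause as the heading of the category: "Any other AEs or SAEs of at least moderate severity that are possibly related to pomalidomide and deemed medically relevant at masked data review". Seven items follow: pulmonary embolism, mouth ulceration, raised alanine aminotransferase, tremor, dyspnoea (with exertional dyspnoea), tachycardia and muscle spasms. The last three repeat the threshold, for example "Muscle spasms (only the cases that meet criteria of at least possibly and at least moderate". The first four are bare terms, for example "Alanine aminotransferase increased".

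SAP 7.5 assigns the masked review to the protocol team, before unblinding. SAP 10.2 separately lists all adverse events and summarises them by class and preferred term, by severity, and by relationship, in each arm. SAP 12 states: "No changes from that specified in the protocol were made".

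**The concern.** The protocol's rule can be applied by anyone who has the severity grade and the causality assessment of each event. The SAP's rule cannot, because it rests on a judgement of relevance for which neither document gives a criterion. SAP 9.2 says that the terms were identified at the blinded review, so the list was drawn up after the pooled events had been seen. Any term left off the list is outside the category, whatever its grade or relatedness.

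Safety and tolerability is the first secondary objective in both documents, and this bullet catches related toxicity that nobody thought to name in advance. Under the SAP it no longer does so by rule. For example, Protocol 2.3.1 names dizziness and confusional state among the known risks of the drug, and no term in SAP 9.2 covers them. The documents do not say whether such events occurred. The SAP simply no longer ensures that they would be counted here.

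A second issue is how to program the four items that do not repeat the threshold.

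**Working it through.** The plan states no incidence, sample size or test for this category, so there is no figure to reproduce and no arithmetic to run. The check compares the wording.

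**Inputs.** Protocol 4.2.2 item 12; SAP 3.2.3, 9.2, 10.2 and 12; the severity grades in Protocol 8.2.1 (Grade 2 is moderate); the causality categories in Protocol 8.2.2; and Protocol 8.3, under which severity and relationship are recorded for each event. I read possibly related as at least possibly related, as the three qualified bullets in SAP 9.2 do.

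**Step 1: conditions.** The protocol has two: at least moderate, and possibly related. The SAP has three: the same two, plus medical relevance. The protocol's set of terms is open. The SAP's is closed at seven items, or eight terms if dyspnoea and exertional dyspnoea are counted separately. Three of the seven repeat the threshold and four do not (3 + 4 = 7).

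**Step 2: where example events go.** These are illustrations, not reported cases.

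| Event | Protocol's residual bullet | SAP 9.2 residual category |
|---|---|---|
| Grade 2, possibly related, unnamed term judged not relevant | In | Out |
| Grade 2, possibly related tachycardia | In | In |
| Grade 1, possibly related tachycardia | Out | Out |
| Grade 1, possibly related tremor | Out | Out if the heading governs; in if the bare term means all cases |
| Grade 3 pulmonary embolism, judged unlikely to be related | Out | Out if the heading governs; in if the bare term means all cases |

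The first row is the narrowing. The last two rows are the ambiguity. The last row has a further consequence. SAP 9.2 lists only portal vein and deep vein thrombosis under venous thromboembolism, a group to which the protocol attaches no relatedness limit. If the heading governs, a pulmonary embolism not judged at least possibly related is therefore in neither row of SAP 9.2.

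**Step 3: does SAP 10.2 supply the missing count?** The event in the first row is in the SAP 10.2 tables. However, the summaries are described as by severity and by relationship, and nothing says that the two are crossed. Suppose that, outside the named groups, a participants in an arm have an event of at least moderate severity and b have one that is at least possibly related. The number with a single event that is both can be anything from 0 to the smaller of a and b, because one participant can have a moderate unrelated event and a mild related one. Separate tables therefore do not give the protocol's category. It could be counted by hand from the event listings, but no planned table is stated to show it.

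**Step 4: disclosure.** Other rows of SAP 9.2 mark what was modified or added at masked review, such as the transfusion outcome, the diary unit and the platelet categories. The residual bullet mentions the review, but nothing identifies the extra condition as a departure from the protocol. SAP 12 reports none.

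**The case against.** The strongest reply has four parts.

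- **The protocol endpoint is open-ended.** Item 12 concerns incidence and severity generally. It defines no composite count and no test for the residual bullet. A reader might infer that the SAP no longer reports the protocol's endpoint at all. The documents do not support that: one category within the endpoint is narrower, and the rest of item 12 is still addressed.
- **Nothing leaves the safety report.** SAP 10.2 lists and tabulates every event in the reportable period, and SAP 10.3 covers serious ones. This stands. What remains is that severity and relationship are not stated to be crossed.
- **The heading covers all seven items.** A reader might infer from the repeated qualifiers that the threshold applies to three of the seven and that mild or unrelated cases of the other four are counted. The text does not establish this, because the heading states the threshold over the whole list. The three repeats may only mean that those terms also had non-qualifying cases when the data were reviewed. The point is an ambiguity for four items, not a demonstrated inconsistency.
- **The choice was masked and carries no formal inference.** The review preceded unblinding, so the arm could not drive it. Protocol 10.4.9 and SAP 7.7 say that other secondary endpoints are not judged for statistical significance. Both stand. A reader might want to express the narrowing as lost power, but that would need event rates that the documents do not give, for a test that neither document specifies.

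None of this answers the undefined third condition, the closed list or the statement in SAP 12.

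**Conclusion.** The point holds as a limited one. The SAP's residual category is narrower than the protocol's, the added condition has no stated criterion, and SAP 12 does not disclose it. An event that is at least moderate and at least possibly related can fall outside the category and then be found only in general tables that are not stated to show the two attributes together. For four of the seven items it is unclear whether the threshold applies.

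The size can be given only in structural terms: two conditions became three, an open set became seven items, and four of those are ambiguous. The documents contain no event counts, so it is not known whether any qualifying event was left out, and no effect on an incidence or an arm difference can be derived. The conclusion rests on reading the protocol bullet literally and possibly related as at least possibly related. It does not rest on any suspicion about how the terms were chosen.

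**What to change.** - **SAP 9.2 (and 3.2.3), the category.** Report by arm the number and percentage of participants with any adverse event or serious adverse event outside the named groups that is Grade 2 or higher and at least possibly related, overall and by preferred term. Keep the terms judged medically relevant as a sub-listing under that row.
- **SAP 9.2, the threshold.** State that both limits apply to every item in the category, including the four that do not repeat them. Also state whether a pulmonary embolism that does not meet the limits is counted under venous thromboembolism or only in the general tables.
- **SAP 12.** If a narrower list is kept as the endpoint category, record it as a change from the protocol, with the basis on which relevance was judged.

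The cost is SAP wording and one extra table row with its breakdown by term. Protocol 8.3 already requires severity and relationship for each event, so no new data are needed. The downside is that the row will include some clinically minor terms, which the sub-listing lets a reader separate.
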